12.7. Resolution

The Investigator will be required to assess the outcome of the AE for investigational product as one of the following:

- Resolved,
- Not Resolved,
- Fatal,
- Resolved with sequelae,
- Resolving, or
- Unknown.

Any causally-related AEs unresolved upon completion of the last study visit will be followed up by the study staff until the event or its sequelae resolve or stabilize at a level acceptable to the Investigator and recorded in the EDC system. An event that is assessed as resolved with sequelae or resolving indicates that the subject has stabilized to a level acceptable to the Investigator and has concurrence by the Sponsor.

12.8. Severity Assessment

The severity of AEs from investigational product will be assessed by the Investigator or medically qualified individual (MD/DO/ DMD/DDS) using the following general categorical descriptors:

MILD: Awareness of symptoms that are easily tolerated, causing minimal discomfort and not interfering with subject's usual function or normal everyday activities
 MODERATE: Sufficient discomfort is present to cause interference to some extent with subject's usual function or normal everyday activity
 SEVERE: Extreme distress, causing significant impairment of functioning or incapacitation; interferes significantly with subject's usual function; prevents normal everyday activities

Note the distinction between the severity and the seriousness of an AE. A severe event is not necessarily a serious event. For example, a headache may be severe (interferes significantly with subject's usual function) but would not be classified as serious unless it met one of the criteria for SAEs, listed above.

COMPANY CONFIDENTIAL 33 of 53

12.9. Causality Assessment

- The Investigator's or medically qualified individual (MD/DO/ DMD/DDS) assessment of causality for investigational product (i.e., relationship to investigational product) must be provided for all AEs (serious and nonserious). An Investigator's causality assessment is the determination of whether there exists a reasonable possibility that the investigational product caused or contributed to an AE.
- Not Related An AE that is not related to the use of the drug
- Doubtful An AE for which an alternative explanation is more likely, e.g., concomitant drug(s), concomitant disease(s), or the relationship in time suggests that a causal relationship to investigational product is unlikely.
- Possible An AE that might be due to the use of the drug. An alternative explanation, e.g., concomitant drug(s), concomitant disease(s), is inconclusive. The relationship in time is reasonable; therefore, the causal relationship to investigational product cannot be excluded.
- Probable An AE that might be due to the use of the drug. The relationship in time is suggestive (e.g., confirmed by dechallenge) and an alternative explanation is less likely, e.g., concomitant drug(s), concomitant disease(s).
- Very Likely An AE that is listed as a possible adverse reaction and cannot be reasonably explained by an alternative explanation, e.g., concomitant drug(s), concomitant disease(s). The relationship in time is very suggestive (e.g., it is confirmed by dechallenge and rechallenge) for a causal relationship to the drug.

If the Investigator determines a SAE is associated with study procedures, the Investigator must record this suspected causal relationship in the source documents and in the EDC system, as appropriate, and report such an assessment in accordance with the SAE reporting requirements, if applicable.

12.9.1. Withdrawal Due to Adverse Events

When a subject withdraws due to a SAE, the SAEs must be reported in accordance with the reporting requirements defined below.

12.9.2. Eliciting Adverse Event Information

The Investigator is to report all directly observed AEs and all AEs spontaneously reported by the study subject. In addition, each study subject will be questioned about AEs.

12.9.3. Reporting Requirements

Each AE is to be assessed to determine if it meets the criteria for a SAE. If a SAE occurs, expedited reporting will follow local and international regulations, as appropriate.

For randomized subjects, all AEs will be reported on the AE source document page and then will be entered in EDC. A Clinical Serious Adverse Event (SAE) Report Form must also be completed if the event is considered to be serious. It should be noted that this Clinical SAE Report Form for collection of SAE information is not the same as the AE EDC page. Where the same data are collected, the forms must be completed in a consistent manner. For example, the same AE term should be used on both

COMPANY CONFIDENTIAL 34 of 53

forms. Adverse events should be reported using concise medical terminology in the EDC system as well as on the form for collection of SAE information.

12.9.3.1. Serious Adverse Event Reporting Requirements

If a SAE occurs, the Sponsor is to be initially notified by telephone immediately upon awareness of the event by the Investigator's site. Within 24 hours of the Investigator site's awareness of the event, the study site must send the Sponsor the Clinical SAE Report Form (via a secure e-mail). This timeframe also applies to additional new information (follow-up) on previously forwarded SAE reports as well as to the initial and follow-up reporting of EIU cases. In the rare event that the Investigator's site does not become aware of the occurrence of a SAE immediately (e.g., if an outpatient study subject initially seeks treatment elsewhere), the Investigator's site is to report the event immediately after learning of it as described and document the time of the study site's first awareness of the AE.

For all SAEs, the Investigator is obligated to pursue and provide information to the Sponsor in accordance with the timeframes for reporting specified above. In addition, an Investigator may be requested by the Sponsor to obtain specific additional follow-up information in an expedited fashion. This information may be more detailed than that captured on the AE case report form. In general, this will include a description of the adverse event in sufficient detail to allow for a complete medical assessment of the case and independent determination of possible causality. Information on other possible causes of the event, such as concomitant medications and illnesses must be provided. In the case of a subject death, a summary of available autopsy findings (if available) and death certificate should be collected if permission is obtained from the subject's family. For a hospitalization, a copy of the hospital discharge summary should be requested. If obtained, these documents (with subject's personal identifiers redacted) should be submitted as soon as possible to the Sponsor or its designated representative.

Appropriate SAE forms will be provided to the study site at the initiation of the study. Upon notification of an SAE at the study site, the Investigator or designated study site staff should call and speak to their Sponsor's study team contact immediately to initially notify them of the SAE.

Within 24 hours of awareness of the event, the Investigator or designated study site staff:

- Complete the Clinical SAE Report Form [that has been provided to you by the Sponsor or their designee] with as much information as possible, however at a minimum, the subject identification number, name of product, SAE, and name of reporter are required);
- Ensures the Investigator signs the Clinical SAE Report Form **prior to** sending to the Sponsor;
- Scans and send via secure email the Clinical SAE Report Form and any supportive documentation to the Sponsor contacts.
- The Sponsor contact information:

COMPANY CONFIDENTIAL 35 of 53

12.10. Special Situations

Special Situations (SS): Safety events that may not meet the definition of an AE; however, are required to be collected to meet Health Authority requirements. Examples include:

- Overdose of a J&J medicinal product.
- Pregnancy exposure (maternal and paternal) to a J&J medicinal product or medical device.
- Exposure to a J&J product from breastfeeding.
- Suspected abuse/misuse of a J&J medicinal product or medical device.
- Inadvertent or accidental exposure to a J&J medicinal product or medical device (including occupational exposure).
- Any failure of expected pharmacological or medical device action (i.e., lack of effect) of a J&J product.
- Unexpected therapeutic or clinical benefit from use of a J&J product.
- Medication error involving a J&J medicinal product or medical device with or without patient/consumer exposure to the J&J product, (e.g., product name confusion) OR that caused an unintended effect or could cause an intended effect (e.g. adult medicine given to a young child).
- Suspected transmission of an infectious agent via a J&J product.
- Off-label use. Note: Off-label use of a product without an associated AE should be collected only when it is specifically and voluntarily brought to the attention of the company in an unsolicited manner by a reporter (e.g., Patient or HCP), or data obtained from databases where off-label use may be systematically collected (e.g., reimbursement database in US), and in accordance with local procedure in compliance with local laws and regulations.

COMPANY CONFIDENTIAL 36 of 53
12.11. Exposure In Utero

For investigational products within clinical studies and for marketed products, an exposure *in utero* EIU occurs if:

- 1. A woman is exposed to the investigational product at any time between her last menses prior to conception through the delivery of the baby.
- 2. There is a possibility of intrauterine exposure to drug via semen from the male partner who is taking the investigational product at the time of conception, thereby possibly exposing the fetus to the product.

If any study subject or study subject's partner becomes or is found to be pregnant during the study subject's participation, the Investigator must report the pregnancy to the Sponsor on a Pregnancy Notification Form (to be provided by the Sponsor when applicable). In addition, the Investigator must submit information regarding environmental exposure to a Sponsor product in a pregnant woman (e.g., a nurse reports that she is pregnant and has been exposed to a cytotoxic product by inhalation or spillage) using the Pregnancy Notification Form. This must be done irrespective of whether an adverse event has occurred and notification must occur within 24 hours of awareness of the pregnancy. Initial notification via telephone to the Sponsor's study team contact must occur immediately upon the Investigator site's awareness of the pregnancy. The Pregnancy Notification Form must then be sent to the Sponsor within 24 hours of the site's awareness. The information submitted should include the anticipated date of delivery (see below for information related to induced termination of pregnancy).

Follow-up is conducted to obtain pregnancy outcome information on all EIU reports. The Investigator will follow the pregnancy until completion or until pregnancy termination (i.e., induced abortion) and then notify the Sponsor of the outcome. The Investigator will provide this information as a follow-up to the initial Drug Exposure During Pregnancy Collection Form A and/or End of Pregnancy Collection Form B (provided by the Sponsor when applicable). The reason(s) for an induced abortion should be specified. An EIU report is not created when an ectopic pregnancy report is received since this pregnancy is not usually viable. Rather, a SAE case is created with the event of ectopic pregnancy.

The Investigator should follow the procedures for reporting SAEs if the outcome of the pregnancy meets the criteria for immediate classification as a SAE (i.e., spontaneous abortion, stillbirth, neonatal death, or congenital anomaly [including that in an aborted fetus, stillbirth, or neonatal death]). In the case of a live birth, the "normality" of the newborn can be assessed at the time of birth (i.e., no minimum follow-up period of a presumably normal infant is required before an End of Pregnancy Collection Form B can be completed). The "normality" of an aborted fetus can be assessed by gross visual inspection, unless pre-abortion test findings are suggestive of a congenital anomaly.

Additional pregnancy outcomes that are classified as SAEs and should be reported as such include:

- "Spontaneous abortion" includes miscarriage and missed abortion.
- All neonatal deaths that occur within 1 month of birth, without regard to causality.
- Any infant death after 1 month that the Investigator assesses as possibly related to *in utero* exposure to the investigational product.

COMPANY CONFIDENTIAL 37 of 53

13. STATISTICS

The Sponsor's **sector of** will be responsible for data management and statistical analyses. Detailed methodology for the statistical analysis of the data will be documented in the Statistical Analysis Plan to be finalized and approved prior to database lock and release of randomization.

13.1. Sample Size Determination

This study is to demonstrate the therapeutic equivalence of the new formulation of to the current formulation based on the change from baseline in redness at 60 seconds after the initial eye drop. To determine the equivalence range, a meta-analysis was conducted. First, a sub-team was established and developed the search criterion and conducted a broad search of historical studies.

13.2. Analysis Sets

13.2.1. Efficacy Analyses Sets

13.2.2. Safety Analysis Set

The safety analysis will be based on all randomized subjects who use at least one dose of investigational product.

13.2.3. Baseline and Demographics

Descriptive statistics (number of subjects, mean, and standard deviation, median, minimum and maximum value for continuous variables; the number and percentage of subjects in each response

COMPANY CONFIDENTIAL 38 of 53

category for categorical variables) will be provided for demographic and baseline characteristics for all randomized subjects by treatment sequence.

13.3. Efficacy Analysis

13.3.1. Primary Endpoint

The change from baseline in redness at 60 seconds after the initial eye drop will be analyzed using the

13.3.2. Secondary Endpoint

The assessment of redness at other time points will be analyzed in the same way as for the analysis of the primary endpoint.

13.4. Statistical Hypothesis

The objective of this study is to demonstrate the equivalence of the test formulation to the control formulation. The statistical hypothesis is stated as

COMPANY CONFIDENTIAL 39 of 53

13.5. Data Computations and Data Imputations

13.5.1. Data Computations

13.5.2. Data Imputations

13.6. Analysis Method

13.6.1. Primary Endpoint

The analysis of primary endpoint is described in section 13.3.1.

13.6.2. Secondary Endpoint

The analyses of secondary endpoints are described in section 13.3.2.

13.6.3. Safety Analysis

The safety analysis will be based on the safety analysis set.

13.6.3.1. Adverse Events

The number and percentage of subjects experiencing treatment emergent AEs and treatment-related AEs will be tabulated by treatment using the MedDRA coding dictionary. Subjects experiencing SAEs will be listed. Treatment-related AEs will include events marked as being at least possibly related to study treatment. Subjects will be counted only once for each system organ class and preferred term.

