9.4. Method of Assigning Subjects to Treatment Groups

As the subjects sign a consent form, (s)he will be sequentially issued a subject ID. The subject ID will begin with the center ID "1001" followed by a four- digit unique subject identifier, e.g. "10011001". Upon qualifying, a unique randomization number will be assigned. This number determines the treatment sequence assignment for each subject according to a randomization schedule. Each subject will be randomized to receive 2 of the 3 Investigational Products, one for each eye. Both products will be packaged in individual subject kits. The product labels will clearly state "LEFT EYE" or "RIGHT EYE". The randomization will be assigned sequentially, from 1-120. Once a randomization number has been assigned to a subject, it cannot be reassigned to another subject. The treatment sequence assignments of the investigational product and control will be based on a randomization scheme devised by the Sponsor. The randomization scheme will be used by the Sponsor to generate the randomization-number-specific single disclosure envelopes.

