6.3 Statistical Methods

Summary statistics will be provided for the efficacy endpoints by treatment.

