6.4.4 Safety Analyses

The safety analysis will be based on the safety analysis set. The adverse events will be summarized using the MedDRA coding dictionary by the following:

- Number and percentage of subjects experiencing treatment-emergent adverse events
- Most common treatment-emergent adverse events (≥5% in one or more treatment sequence).
- Number and percentage of subjects with treatment-emergent adverse events by severity

Treatment-emergent adverse events are those with a start date and time on or after the date and time of study dose administration.

The number of subjects with treatment-emergent adverse events will also be summarized by sex, age group (18-64 years, \geq 65 years) and race (white, non-white).

- Number and percentage of subjects who discontinued the trial due to adverse events
- Number and percentage of subjects experiencing a serious adverse event
- Number and percentage of subjects experiencing treatment-related adverse events (relationship to study medication is marked as possible, probable or very likely)

[figure not shown]
AEs with unknown relationship to treatment will be counted as treatment-related.

• Number and percentage of subjects with treatment-related adverse events by severity.

Subjects will be counted only once for each system organ class and preferred term.

APPENDICES

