14.3.2 Subjects with Treatment-Emergent Adverse Events (Safety Analysis Set)

Table 14.3.2 (Page 1 of x)
Subjects with Treatment-Emergent Adverse Events [1]
Safety Analysis Set

	A/B	A/C	B/C	Total	
	(N=xx)	(N=xx)	(N=xx)	(N=xx)	
System Organ Class Preferred Term	n (%)	n (%)	n (%)	n (%)	
SUBJECTS WITH AT LEAST ONE AE	xx(x.x%)	xx(x.x%)	xx(x.x%)	xx (xx.x%)	
BODY SYSTEM 1 ADVERSE EVENT 1 ADVERSE EVENT 2	x(x.x%)	x(x.x%)	x(x.x%)	xx (xx.x%)	
	x(x.x%)	x(x.x%)	x(x.x%)	xx (xx.x%)	
	x(x.x%)	x(x.x%)	x(x.x%)	xx (xx.x%)	
BODY SYSTEM 2 ADVERSE EVENT 3 ADVERSE EVENT 4	x(x.x%)	x(x.x%)	x(x.x%)	xx (xx.x%)	
	x(x.x%)	x(x.x%)	x(x.x%)	xx (xx.x%)	
	x(x.x%)	x(x.x%)	x(x.x%)	xx (xx.x%)	

. . .

A: , Tetrahydrozoline 0.05% B: e 0.05%, Glycerin 0.40%

C: Tetrahydrozoline 0.05%, Glycerin 0.20%, Hypromellose 0.2%, Polyethylene glycol 400 1.0% Note: AEs are coded by MedDRA Dictionary version 16.x.

^[1] Subjects were counted only once for each system organ class and preferred term.

System Organ Class and Preferred Terms listed in descending order of frequency reported by all subjects within System Organ Class.

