14.3.5 Summary of Treatment-Emergent Adverse Events by Severity (Safety Analysis Set)

 $\begin{array}{c} \text{Table 14.3.5 (Page 1 of x)} \\ \text{Summary of Treatment-emergent Adverse Events by Severity} \\ \text{Safety Analysis Set} \end{array}$

	======================================		 A/C			B/C		
	(N=xx)			(N=xx)			(N=xx)	
System Organ Class Preferred Term	Mild Moderat n (%) n (%)	e Severe n (%)	Mild n (%)	Moderate n (%)	Severe n (%)	Mild n (%)	Moderate n (%)	Severe n (%)
SUBJECTS WITH AT LEAST ONE AE	xx(x.x%) xx(x.x%) xx(x.x%)	xx(x.x%)	xx(x.x%)	xx(x.x%)	xx(x.x%)	xx(x.x%)	xx(x.x%)
BODY SYSTEM 1 ADVERSE EVENT 1 ADVERSE EVENT 2	%x.x) x (%x.x) x %x.x) x (%x.x) x x(x.x) x (%x.x)) x(x.x%)	x(x.x%) x(x.x%) x(x.x%)	x(x.x%) x(x.x%) x(x.x%)	x(x.x%) x(x.x%) x(x.x%)	x(x.x%) x(x.x%) x(x.x%)	x(x.x%) x(x.x%) x(x.x%)	x(x.x%) x(x.x%) x(x.x%)
BODY SYSTEM 2 ADVERSE EVENT 3 ADVERSE EVENT 4	x(x.x%) x(x.x% x(x.x%) x(x.x% x(x.x%) x(x.x%) x(x.x%)	x(x.x%) x(x.x%) x(x.x%)	x(x.x%) x(x.x%) x(x.x%)	x(x.x%) x(x.x%) x(x.x%)	x(x.x%) x(x.x%) x(x.x%)	x(x.x%) x(x.x%) x(x.x%)	x(x.x%) x(x.x%) x(x.x%)

MedDRA Coding Dictionary version 18.0.

⁻⁻⁻⁻

[:] Tetrahydrozoline 0.05%

e 0.05%, Glycerin 0.40%

C: Tetrahydrozoline 0.05%, Glycerin 0.20%, Hypromellose 0.2%, Polyethylene glycol 400 1.0%

Subjects are counted only once for each system organ class and preferred term by selecting the most severe event. Listed in descending order of frequency reported by all subjects within System Organ Class.

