16.1.7 Randomization Schedule (All Randomized Subjects)

Listing 16.1.7 (Page 1 of x)
Randomization Schedule
All Randomized Subjects

Randomization Number	Subject ID	Treatment Sequence	Eye	Treatment Code	Treatment Description	=======================================
001	xxxxxxx	АВ	Left Right	А В		, Tetrahydrozoline 0.05% e 0.05%, Glycerin 0.40%

16.2.1.1 **Subject Disposition Listing (All randomized Subjects)**

Listing 16.2.1.1 (Page 1 of 3) Subject Disposition Listing All Randomized Subjects

						Treatme	nt
Treatment Sequence	Subject ID	Intent- to-Treat Subjects	Safety Analysis Set	Date Completed/ Withdrew	Study Completion/ Discontinuation Reason	Date First Use	Date Last Use
AB	xxxxxxx	Yes	Yes	14DEC2011	COMPLETED	21SEP2011	040CT2011

A: , Tetrahydrozoline 0.05% B: e 0.05%, Glycerin 0.40% C: Tetrahydrozoline 0.05%, Glycerin 0.20%. Hypromellose 0.2%, Polyethylene glycol 400 1.0%

16.2.1.2 **Discontinued Subjects (All randomized Subjects)**

Listing 16.2.1.2 (Page 1 of 1) Discontinued Subjects All Randomized Subjects

						Treatm	ment
Treatment Sequence	Subject ID	Intent- to-Treat Subjects	Safety Analysis Set	Date Completed/ Withdrew	Study Completion/ Discontinuation Reason	Date First Use	Date Last Use
AB	xxxxxxx	Yes	Yes	14DEC2011	DISCONTINUED	21SEP2011	040CT2011

⁻⁻⁻

A:
B:
C: Tetrahydrozoline 0.05%
e 0.05%, Glycerin 0.40%
C: Tetrahydrozoline 0.05%, Glycerin 0.20%. Hypromellose 0.2%, Polyethylene glycol 400 1.0%

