AB	xxxxxxx xxxxxxx xxxxxxx	XXXXXXXX XXXXXXXX XXXXXXXX	xxx-xx-xx xxxx-xx-xx xxxx-xx-xx	xxx-xx-xx xxxx-xx-xx	No No No
• • •					

[,] Tetrahydrozoline 0.05%

E: e 0.05%, Glycerin 0.40% C: Tetrahydrozoline 0.05%, Glycerin 0.20%. Hypromellose 0.2%, Polyethylene glycol 400 1.0%

16.2.6.1 **Ocular Redness Assessment (All randomized Subjects)**

Listing 16.2.6.1 (Page 1 of 3) Ocular Redness Assessment All Randomized Subjects

Treatment Sequence	Subject ID	Assessment Time Point	Right Eye	Treatment	Redness Assessment	Reduction from Baseline	Responder?	Start Date	End Date
AB	xxxxxxx xxxxxxx xxxxxxx	0s 0s 30s 30s	Right Left Right Left	А В А В	2.5 2.0 1.0 1.0	1.5 1.0	Yes Yes	xxx-xx-xx xxxx-xx-xx xxxx-xx-xx	xxxx-xx-xx xxxx-xx-xx xxxx-xx-xx

A: Tetrahydrozoline 0.05% B: e 0.05%, Glycerin 0.40%

C: Tetrahydrozoline 0.05%, Glycerin 0.20%. Hypromellose 0.2%, Polyethylene glycol 400 1.0% Assessment time point:

Os = Pre-Treatment prior to the first product application (Baseline),

³⁰s = 30 seconds after the first product application, 60s = 60 seconds after the first product application,

¹²⁰s = 2 minutes after the first product application.

Redness Assessment: 0 = None, 1 = Mild, 2= Moderate, 3 = Severe, 4 = Extremely Severe.

16.2.6.2 **Ocular Comfort Assessment (All randomized Subjects)**

Listing 16.2.6.2 (Page 1 of 3) Ocular Comfort Assessment All Randomized Subjects

Treatment Sequence	Subject ID	Assessment Time Point	Right Eye	Treatment	Comfort Assessment	Reduction from Baseline	Start Date	End Date
AB	XXXXXXXX	0s	Right	A	2.5		xxxx-xx	xxxx-xx-xx
	XXXXXXX	0s	Left	В	2.0		XXXX-XX-XX	XXXX-XX-XX
	XXXXXXX	60s	Right	A	1.0	1.5	xxxx-xx-xx	XXXX-XX-XX
	XXXXXXX	60s	Left	В	1.0	1.0	xxxx-xx-xx	XXXX-XX-XX

A: Tetrahydrozoline 0.05% B: e 0.05%, Glycerin 0.40%

C: Tetrahydrozoline 0.05%, Glycerin 0.20%. Hypromellose 0.2%, Polyethylene glycol 400 1.0% Assessment time point:

Os = Pre-Treatment prior to the first product application (Baseline),

⁶⁰s = Following the 60 second ocular Redness Assessment;

¹⁰h = 10 hours after the 1st product application,

¹²h = 12 hours after the 1st product application. Comfort Assessment: 0 = Very Uncomfortable, 10 = Very Comfortable.

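### The protocol tabulates adverse events by treatment, but every SAP adverse-event table uses product-pair columns, so no planned output gives an ocular adverse-event rate for a single product (minor)

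*Protocol*

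**What the plan says.** Protocol 9.4 sets the design: "Each subject will be randomized to receive 2 of the 3 Investigational Products, one for each eye". Protocol 13.6.3.1 then says of safety: "The number and percentage of subjects experiencing treatment emergent AEs and treatment-related AEs will be tabulated by treatment using the MedDRA coding dictionary". Protocol 13.2.3 groups demographics differently, by treatment sequence.

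SAP 6.3 uses the protocol's AE grouping term for efficacy: "Summary statistics will be provided for the efficacy endpoints by treatment". The shells that follow (Tables 14.2.1.1 to 14.2.3: redness, comfort, questionnaire) have one column per product.

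For AEs, SAP 6.4.4 names no by-treatment grouping. Its only reference to treatment columns is the cut-off for common events, "5% in one or more treatment sequence". Tables 14.3.1 to 14.3.9 all have columns A/B, A/C and B/C, where A is the marketed control and B and C are the two new formulations. Seven add a Total; the two severity tables, 14.3.5 and 14.3.9, do not. AE Listings 16.2.7.1 to 16.2.7.3 give the treatment sequence but no eye and no product. Eye and product do appear together in Listing 16.1.7 and in the redness, comfort and questionnaire Listings 16.2.6.1 to 16.2.6.3.

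**The concern.** The trial compares two new eye-drop formulations with a marketed one, and the introduction gives the wish for an alternative to a preservative as the reason. How often each product is followed by an ocular event is an obvious descriptive safety question, and the two-eye design can answer it directly. A pair column counts a subject whichever of two products was in the affected eye, so it does not give a rate for either one. The listings do not fill the gap: a reader would have to find the eye in the free-text event description, if it is there, and merge by hand with the randomization listing. At stake is how clearly and precisely ocular safety is described by product. The equivalence conclusion is not involved.

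**Working it through.** The plan states no figure on this point to reproduce. The check has a textual part and an illustrative part.

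**Layout, side by side**
- Protocol 13.6.3.1: AEs by treatment. Protocol 13.2.3: demographics by treatment sequence. The protocol thus uses two terms.
- SAP 6.3 and Tables 14.2.1.1 to 14.2.3: by treatment means one column per product.
- SAP 6.4.4 and Tables 14.3.1 to 14.3.9: pair columns only. No AE shell has a column for A, B or C alone, and a Total pools all three pairs.
- The sequence label does not safely supply the eye. For AB, the sample row of Listing 16.1.7 has A in the left eye, and the sample rows of Listing 16.2.6.1 have A in the right eye. These are mock rows, so this is not an error, but it shows that the label alone is not enough.

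**Bases**
- 120 subjects are randomized (Protocol synopsis), two products each. An equal split across pairs is assumed; the documents call the design balanced but give no counts per pair.
- Subjects per pair: 120 / 3 = 40. Subjects exposed per product: 120 × 2 / 3 = 80.

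**What a pair column leaves open**
- Suppose each pair column shows 4/40. Product A occurs in A/B and A/C, so its own count lies anywhere from 0/80 (every event in the other product's eye) to 4 + 4 = 8/80.

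**Comparing C with A (illustrative risks A 2%, B 2%, C 10%; independent eyes)**
- Pair risk = 1 − (1 − p₁)(1 − p₂).
- A/B: 1 − 0.98 × 0.98 = 3.96%. B/C: 1 − 0.98 × 0.90 = 11.8%. A/C is also 11.8%.
- B/C minus A/B: 11.8 − 3.96 = 7.84 points, against a true difference of 8. If susceptibility is fully shared between eyes, so that the pair risk is the larger of the two, it is 10 − 2 = 8 points.
- SD of that contrast: √(0.118 × 0.882/40 + 0.0396 × 0.9604/40) = √0.003553 = 6.0 points.
- SD from direct product columns: √(0.10 × 0.90/80 + 0.02 × 0.98/80) = √0.001370 = 3.7 points, if every event is assigned to an eye.
- Most of the loss is the smaller base. The direct formula with 40 in place of 80 gives √0.002740 = 5.2 points; the rest comes from events under the shared product B.

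**The case against.** **The wording conflict is soft.** SAP 6.4.1 summarizes medical history by treatment group while its shell, Table 14.1.4, has pair columns, and the title of Table 14.3.4 calls the pairs treatment groups. Protocol section 13 also leaves detailed methodology to the SAP. This stands in part. The mismatch may be one of terms, and a protocol amendment is not required. The planned output lacks product columns under either reading.

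**Pairs are the right unit for some events.** Subjects are counted once per term, and a non-ocular event cannot be assigned to one eye's product. This stands, and it limits the point to ocular events.

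**A reader might infer that the new formulations cannot be compared with the control at all.** The documents do not support that. A/B and B/C share product B, so their contrast is a randomized comparison of C with A; A/C and B/C likewise compare A with B. Neither needs independent eyes to show a difference. An assumption about how events in the two eyes are related is needed only to recover absolute rates for a product, and the plan proposes no such calculation.

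**A reader might also infer that the 5% rule distorts or conceals safety findings.** The cut-off is 2 of 40 by pair and 4 of 80 by product, so the two bases can select different terms. It is only a display threshold, and Table 14.3.2 lists every treatment-emergent term.

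**The AE page is not in the documents shown**, so the eye may already be recorded. This stands, and that part of the fix is conditional.

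**Conclusion.** The point holds as a minor one. No planned AE table or listing gives an ocular AE rate by product, although Protocol 13.6.3.1, read alongside the protocol's and SAP's other uses of the terms, suggests that one was intended. Product differences can still be seen by contrasting pair columns, with an SD of about 6.0 points where direct product columns would give 3.7. Those two figures rest on an equal split of 120 subjects, independent eyes and illustrative risks that are not in the documents; the second also needs every event to be assigned to an eye. The finding about the layout needs none of these assumptions. The effect is confined to descriptive safety output: no term is lost and the equivalence conclusion is unchanged.

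**What to change.** - In SAP 6.4.4, add tables of ocular treatment-emergent and ocular treatment-related AEs by the product in the affected eye. Use three product columns, with the subjects exposed to each product as denominator (about 80). Count a bilateral event once under each product, and add a footnote that the columns do not sum to the number of subjects.
- Keep the pair columns for non-ocular AEs.
- Add eye and product columns to Listings 16.2.7.1 to 16.2.7.3.
- Record the affected eye (left, right or both) if the AE page does not already do so. This has to happen during the study, because it may not be recoverable afterwards.
- Define by treatment in the SAP (ocular by product, non-ocular by pair) so that it agrees with Protocol 13.6.3.1. Rewording the protocol is optional.

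The cost is a short SAP change, a few extra shells, two listing columns and possibly one AE field. A small drawback is that the product columns exceed the subject total, which the footnote explains. No extra subjects or visits are needed.
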